13.3 Stratification Factors

n/a

13.4 Interim Monitoring Plan

The study will be referred to the DSMC for review of dosing and toxicity at the first occurrence of a toxic death.

13.5 Analysis of Primary Endpoints

The primary endpoint will be the proportion of responders. A responder is defined as an eligible, evaluable participant who achieves either complete resolution or regression of disease, per section 7, as the best overall response at any point during study therapy.

13.6 Analysis of Secondary Endpoints

Secondary endpoints are

- a) Duration of response defined as the time elapsing between the documentation of the onset of remission until clinical and/or radiographic evidence of progression.
- b) Progression-free survival (PFS), where time to event for PFS is the time from study enrollment until the time of first occurrence of new lesions, progressive disease, or death from any cause, or until last contact if no event occurs;
- c) Overall survival (OS), calculated as the time from enrollment until death or last contact; and,
- d) The proportion of participants reporting grades 3-4 toxicity, for each CTC v4 toxicity code
- e) Serial quantification of BRAF mutation in urine and plasma cell free DNA in patients with an identifiable BRAF mutation at baseline.
- f) Serial quantification of serum TNF-alpha levels in all patients, even if not elevated at baseline.

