1. OBJECTIVES

This is an open-label phase II study to evaluate the efficacy and safety of lenalidomide in participants with relapsed/refractory ECD or LCH and in any patient with HS requiring systemic therapy. Patients will receive up to 12 cycles of lenalidomide with treatment occurring on days 1-21 of each 28 day cycle. In cycle one patients will receive lenalidomide 10 mg daily due to the unknown incidence of tumor flare in this population (tumor flare has been observed in other diseases such as chronic lymphocytic leukemia). Patients who tolerate the 10 mg dose well will be escalated to 25 mg for future cycles. There will also be the possibility of dose reduction for patients who do not tolerate the 10 mg starting dose. Dosage thereafter will be adjusted based upon toxicity. Lenalidomide is known to increase the risk of venous and arterial thromboembolic events. Patients not already receiving systemic anticoagulation for other clinical indications will be required to take aspirin 325 mg daily for the duration of the protocol or for one month following treatment discontinuation, whichever is longer.

Disease assessments will occur at baseline and then again at cycle 3 day 1, cycle 6 day 1, cycle 9 day 1 and cycle 12 day 1 as well as every 3 months thereafter until month 24 from study initiation when disease assessment will occur every 6 months until month 36 from the initiation of treatment. Disease assessments will consist initially of an MRI of the brain/pituitary and PET/CT (although a CT of the chest, abdomen and pelvis along with a bone scan is allowed if PET/CT is rejected by insurance). Clinical documentation of skin lesions with photography is highly encouraged. Measurement and documentation of all skin lesions is required even if photography is not performed. A repeat MRI is not required beyond baseline if the MRI at baseline is normal and there is no clinical suspicion of CNS or pituitary involvement. A bone marrow biopsy is only required if the patient has at least one cytopenia of grade 2 or greater at baseline or has evidence of bone marrow involvement on PET/CT. The bone marrow biopsy only needs to be repeated if abnormal at baseline.

Patients will be followed for 3 years (thirty-six months) from the initiation of therapy or until they initiate a new therapy for their underlying disease, whichever occurs first.

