1.3 Secondary Objectives

- To define the progression free survival (PFS) after treatment with lenalidomide
- To define the overall survival (OS) after treatment with lenalidomide
- To describe the safety profile of lenalidomide in LCH, ECD, and HS
- To assess quantitative changes in urinary and plasma cell free DNA harboring the BRAF V600E mutation and correlate the presence or absence of the BRAF V600E mutation with response
- To assess serial changes in TNF-alpha levels in patients treated with lenalidomide
- To assess the mutational landscape of these diseases using Oncopanel

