6. DOSING DELAYS/DOSE MODIFICATIONS

Dose delays and modifications will be made as indicated in the following table(s). The descriptions and grading scales found in the revised NCI Common Terminology Criteria for Adverse Events (CTCAE) version 4.03 will be utilized for dose delays and dose modifications and version 3.0 should be used for tumor flare. A copy of the CTCAE version 4.0 can be downloaded from the CTEP website

http://ctep.cancer.gov/protocolDevelopment/electronic applications/ctc.htm.

Note that tumor flare reaction is managed differently from other AEs as outlined in Table 4. Lenalidomide should be held for any grade 3 or higher toxicity except in the incidence of a blistering skin rash, in which case lenalidomide should be permanently discontinued though patients will be followed for resolution of toxicity and for survival. In the event of a blistering skin rash the patient should have an urgent dermatology referral if grade 1 or 2 and should be hospitalized if grade 3 or 4. If a patient develops venous thromboembolism and/or pulmonary embolism while on therapeutic anticoagulation lenalidomide treatment should be permanently discontinued regardless of grade unless anticoagulation dosing was low (e.g., INR or anti-factor Xa was not in the generally accepted therapeutic range). Patients experiencing a venous thromboembolic event while on aspirin alone may stay on protocol at the discretion of the treating physician as long as the patient is subsequently on systemic anticoagulation with warfarin, low molecular weight heparin or equivalent for the duration of the study and as clinically indicated thereafter by the nature and extent of the thrombotic event. Patients experiencing an arterial thromboembolic event will be removed from study regardless of the anticoagulation status at the time of the event.

Per table 2, participants may be dose reduced if toxicities occur during cycle 1 at the starting dose of 10 mg daily. No more than 2 dose reductions will be permitted. If the participant cannot tolerate therapy after 2 dose reductions they should be permanently removed from the protocol.

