7.1 Adverse Event List(s) for lenalidomide

The most frequently reported adverse events reported during clinical studies with lenalidomide in oncologic and non-oncologic indications, regardless of presumed relationship to study medication include: anemia, neutropenia, thrombocytopenia and pancytopenia, abdominal pain, nausea, vomiting and diarrhea, dehydration, rash, itching, infections, sepsis, pneumonia, UTI, Upper respiratory infection, atrial fibrillation, congestive heart failure, myocardial infarction,

chest pain, weakness, hypotension, hypercalcemia, hyperglycemia, back pain, bone pain, generalized pain, dizziness, mental status changes, syncope, renal failure, dyspnea, pleural effusion, pulmonary embolism, deep vein thrombosis, CVA, convulsions, dizziness, spinal cord compression, syncope, disease progression, death not specified and fractures.

Second New Cancers

In clinical studies of newly diagnosed multiple myeloma, a higher number of second cancers were reported in patients treated with lenalidomide as induction therapy (treatment for several cycles to reduce number of cancer cells) and/or bone marrow transplant followed by lenalidomide for a long period of time compared to patients treated with induction therapy and/or bone marrow transplant then placebo (a capsule containing no lenalidomide). Patients should make their doctors aware of their medical history and any concerns they may have regarding their own increased risk of other cancers.

Tumor Flare

Tumor flare assessments are conducted in Cycle 1 on Days 1, 8, and 15 (±1 day), and when clinically indicated thereafter. Tumor flare reaction (TFR) is defined in the NCI-CTCAE version 3 as a constellation of signs and symptoms of tumor pain, inflammation of visible tumor, hypercalcemia, diffuse bone pain, and other electrolyte disturbances in direct relation to initiation of therapy (Cancer therapy evaluation program, 2003).

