- CBC with automated differential will be checked every 7 days (+/- 1 day) during cycles 1 and 2; local labs are acceptable. Labs only necessary if dose escalation occurs. Note, these labs can be obtained at a local laboratory. Window for labs is +/- 3 days. k:
- Window for end of treatment visit is +/-7 days from the date of last dose. 1:
- The first follow up visit will occur 3 months from the date of last dose and then every 3 months thereafter. Window for follow up visits is m: +/- 2 weeks.

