13. STATISTICAL CONSIDERATIONS

13.1 Study Design/Endpoints

The primary endpoint of this study is to evaluate the overall response rate of lenalidomide in patients with LCH. This is a pilot study with a planned accrual of 12 patients. A small sample size was selected due to the rarity of the disease and the difficulty in accruing a larger number of patients at a single center.

Study treatment will be considered worthy of further evaluation if at least three (25%) of 12 patients experience a response. The 90% exact binomial confidence limits for three responses in 12 patients is 7-53%. We will consider a response rate of 5% unworthy of further study for this patient population, and note that two responses in 12 patients is the maximum number of responses which still includes the unworthy response rate of 5% in its confidence limits.

The limited sample size may cause us to miss a small but potentially clinically meaningful response rate or to overestimate the response rate. We are willing to accept this in order to complete the trial in a reasonable time period while recognizing that the results of this trial will be used to determine whether a larger phase II trial of lenalidomide is warranted in which case such a trial would be proposed to the Histiocytosis Society.

Secondary endpoints will include:

- Duration of response
- Progression free survival

- Overall survival
- Description of toxicity
- Quantitative serial measurements of urine and plasma cell free DNA for BRAF mutation as a biomarker of response
- Quantitative serial measurements of serum TNF-alpha levels as a biomarker of response

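### The toxicity analysis in 13.6(d) stops at grade 4, so it omits fatal toxicity; it also leaves tumor flare without a clear place, and 7.1 and the calendar disagree on the Day 8 flare check

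*Combined protocol and SAP*

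**What the plan says.** **Objective and endpoint.** Section 1.3 sets a secondary safety objective with no grade limit: "To describe the safety profile of lenalidomide in LCH, ECD, and HS". Section 13.1 lists the matching endpoint only as "Description of toxicity". Section 13.6(d) is where it becomes an analysis: "The proportion of participants reporting grades 3-4 toxicity, for each CTC v4 toxicity code". Under 13.7.1, everyone who takes at least one dose is evaluable for toxicity.

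**Fatal toxicity.** Section 13.4 provides for it as a monitoring trigger: "The study will be referred to the DSMC for review of dosing and toxicity at the first occurrence of a toxic death".

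**Tumor flare.** Section 1 starts cycle 1 at "lenalidomide 10 mg daily due to the unknown incidence of tumor flare in this population". Section 6, on dose delays and modifications, grades events with CTCAE v4.03 but adds that "version 3.0 should be used for tumor flare". Section 7.1 also takes its definition of flare from version 3. Section 7.2 (v4.0) and Appendix B (v4.03) name version 4 for adverse event reporting and make no exception for flare.

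**Timing of flare checks.** Section 7.1 states: "Tumor flare assessments are conducted in Cycle 1 on Days 1, 8, and 15 (±1 day), and when clinically indicated thereafter". In the section 10 calendar the cycle 1 columns are Day 1 and Day 15 only, and no row is labelled for flare. The one calendar item that falls near Day 8 is in footnote j: "CBC with automated differential will be checked every 7 days (+/- 1 day) during cycles 1 and 2; local labs are acceptable".

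**The concern.** The analysis is narrower than the objective it serves. A safety table that stops at grade 4 leaves out the most severe outcome, and it does so in a trial whose monitoring plan expects that a toxic death could happen. With 12 patients, a single event changes what the table says.

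Flare is the second gap. Its unknown incidence is the stated reason for the cautious first cycle, yet no listed analysis reports how often it occurred. Low-grade flare is cut off by the grade limit. Higher-grade flare is graded on a different CTCAE version from the one that organises the table.

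The calendar disagreement is a separate matter, of consistency rather than analysis. A site working from the calendar would not find the Day 8 flare check that 7.1 sets. Section 7.1 says that nearly all flares begin within the first two to three weeks of cycle 1 and usually resolve in one to two weeks, so the timing of the checks bears on what is observed.

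**Working it through.** **1. The plan's own figure.** The documents give no number for the safety endpoint. The nearest figure is the precision statement in 13.1: 3 responses in 12 patients, 90% exact limits 7-53%. The exact (Clopper-Pearson) limits for x events in n are the beta quantiles B(0.05; x, n-x+1) and B(0.95; x+1, n-x). For x = 3 and n = 12 they are 7.2% and 52.7%, so the stated figure reproduces. The same method is used below.

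**2. One toxic death in 12 (illustration).** Inputs: n = 12 (13.2), all treated (13.7.1). Assumptions: the death is coded grade 5, and no participant has a grade 3-4 event under the same code.

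- As 13.6(d) is written: 0/12 = 0%. The upper limit is 1 - 0.05^(1/12) = 22%, so the 90% exact CI is 0-22%.
- Counting grades 3-5: 1/12 = 8.3%. The lower limit is 1 - 0.95^(1/12) = 0.4%. The upper limit is B(0.95; 2, 11) = 34%. The 90% exact CI is 0.4-34%.

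**3. How likely the case is to arise.** The documents give no rate of fatal toxicity, so a range is assumed. The chance of at least one event in 12 is 1 - (1 - p)^12.

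| Assumed true rate p | Chance of at least one in 12 |
|---|---|
| 1% | 11% |
| 2% | 22% |
| 5% | 46% |
| 10% | 72% |

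**4. Whether another section supplies the missing proportion.**

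- OS and PFS (11.1.4, 13.6) count deaths from any cause and do not separate toxic ones.
- SAE reporting (7.3) and the DSMC provisions (12.2, 13.4) concern notification and oversight.
- 13.1 names the endpoint but specifies no summary.

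None of these gives a proportion with fatal toxicity.

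**5. Tumor flare, by grade.**

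- Grades 1-2: outside 13.6(d) because of the grade limit, whichever version is used.
- Grades 3-4: inside the grade limit, but the version is unsettled. Sections 6 and 7.1 point to v3.0; 7.2, Appendix B and 13.6(d) point to v4. The documents do not say whether v4 has a flare code.

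**6. Flare assessment days in cycle 1.**

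| Source | Day 1 | Day 8 | Day 15 |
|---|---|---|---|
| Section 7.1 | flare assessment | flare assessment | flare assessment |
| Section 10 columns | yes | none | yes |
| Section 10 flare row | none | none | none |

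The adverse event evaluation row shows one mark during treatment. It may be a merged cell that the text extraction broke, but it would not create a Day 8 visit.

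**The case against.** The strongest reply is that nothing would be hidden. Section 7.5 sends all adverse events to the toxicity case report forms. SAEs go to the Overall PI and, within 24 hours, to the drug supplier (7.3). A death counts in OS and PFS, and a first toxic death goes to the DSMC. The 13.1 wording is broad enough to cover a narrative of any fatal event, and in 12 patients such a narrative is likely. All of this stands, and it limits the point to the analysis definition. It does not remove the point, because 13.6(d) is the only prespecified toxicity summary and it would still omit the death.

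Three stronger readings are tempting, and the documents do not support them:

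- *Flare of every grade would be reported as zero.* That needs CTC v4 to have no flare code, which the documents nowhere say. The v3.0 instruction in section 6 is written for dose delays and modifications, and 7.2 and Appendix B would let grade 3-4 flare be reported under v4. Component signs such as pain or hypercalcemia could also be coded there. Only the loss of grade 1-2 flare is certain.
- *The 10 mg cycle exists to estimate flare incidence.* Section 1 presents it as a precaution. Flare incidence is neither an objective in 1.3 nor an endpoint in 13.1.
- *A flare between Day 1 and Day 15 would go unseen.* Section 7.1 itself sets a Day 8 assessment, 5.1 adds a toxicity assessment between Days 22 and 28, and all adverse events are recorded. The two sections conflict; missed events do not follow from that.

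**Conclusion.** The point holds as a defect in how the safety analysis is defined. Read literally, 13.6(d) omits fatal toxicity and grade 1-2 flare, and it leaves the place of grade 3-4 flare unclear. In the one-death illustration the table shows 0/12 where 1/12 (8.3%, 90% exact CI 0.4-34%) is the informative figure. This rests on coding a fatal toxicity as grade 5 and on no grade 3-4 event under the same code; the event count itself is hypothetical.

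A reader might infer that the safety objective would be answered wrongly. The documents support only that it would be answered incompletely, since the data are collected and deaths are reviewed. The sample size, the response rule and the primary result are unaffected. The contradiction between 7.1 and section 10 over Day 8 is real and separate.

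**What to change.** 1. Redefine 13.6(d) as the proportion of treated participants with grade 3-5 toxicity for each CTCAE v4.03 term, with fatal toxicity listed separately.
2. Add to 13.6 the proportion of treated participants with tumor flare, by CTCAE v3.0 grade, including grades 1-2. Exact 90% limits would match the method in 13.1.
3. State in 7.2 and Appendix B which CTCAE version applies to flare for adverse event reporting, so that they agree with sections 6 and 7.1.
4. Reconcile 7.1 with the section 10 calendar on the cycle 1 Day 8 flare assessment. Which of the two should change is for the investigators to decide.

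The cost is a few sentences of text and one or two extra table rows. Items 1 to 3 need no new data, and no item changes the sample size or the decision rule.

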13.7 Reporting and Exclusions

13.7.1 Evaluation of Toxicity

All patients receiving at least one dose of lenalidomide will be evaluable for toxicity

13.7.2 Evaluation of the Primary Efficacy Endpoint

All participants included in the study who receive at least one dose of lenalidomide will be assessed for response to treatment, even if there are major protocol treatment deviations.

2	In bed >50% of the time. Capable		Disabled, requires special care and assistance.
3	to bed or chair more than 50% of waking hours.	30	Severely disabled, hospitalization indicated. Death not imminent.
4	100% bedridden. Completely disabled. Cannot carry on any	20	Very sick, hospitalization indicated. Death not imminent.
4	self-care. Totally confined to bed or chair.	10	Moribund, fatal processes progressing rapidly.
5	Dead.	0	Dead.

APPENDIX B

NCI CTC Version 4.03

Toxicity will be scored using NCI CTC Version 4.03 for toxicity and adverse event reporting. A copy of the NCI CTC Version 4.03 can be downloaded from the CTEP homepage: (http://ctep.info.nih.gov). All appropriate treatment areas have access to a copy of the CTC Version.

APPENDIX C

SOP plasma preparation for EDTA & Streck tubes

NOTE: Time period from draw to freezing of plasma must be less than 3 hours.

1. Draw venous blood into one (1) 10 mL tubes (either EDTA or Streck) labeled CFDNA and immediately gently invert the tubes 8-10 times. Write the patient and draw date number on the tube.

2. Immediately centrifuge for 10 minutes at 1500 (+\- 150) x g. NOTE: Brake switch must be off so the cell/plasma interface is not disturbed.

3. Pipette the plasma layer into a 15 mL tube labeled "CFDNA/with patient #". Do not ship. NOTE: Do not dip the tip of the pipette into the plasma/cell interface. Leave a thin plasma layer intact over the interface.

4. Centrifuge the 15 mL tube containing the plasma only for 10 minutes at 3000 (+/- 150) x g.

5. Transfer using a fresh pipette, the supernatant into a second 15 mL tube labeled "CFDNA super.do not ship". NOTE: Leave about 0.3 mL of supernatant in the centrifuged 15 mL tube. This leftover 0.3 mL contains cellular debris.

6. Using a fresh pipette, transfer 1 mL of plasma from the "super.do not ship" tube into max four (4) 2 mL cryovials labeled CFDNA.ship.patient#/

7. Freeze immediately upright at -70°C or colder until shipping.
